	
heterogeneity, etc.).
 
The Kenward-Roger approximation will be used to estimate denominator degrees of freedom.
 
Significance tests will be based on least squares means and Type III tests.

Participant Disposition	
A detailed description of participant disposition will be provided, including a summary of the number and percentage of participants entered into the study and randomized, and number and percentage of participants who complete the study or discontinue, both overall and by reason for discontinuation. A summary of important protocol deviations will be provided.

Participant Characteristics	
Demographic data are collected and responded to demonstrate that the study population represents the target patient population. A summary of baseline participant characteristics, historical diagnoses, preexisting conditions, and prior therapies will be reported by treatment group using descriptive statistics. Other participant characteristics will be summarized by treatment group as deemed appropriate.

Concomitant Therapy	
Previous and concomitant medications will be summarized by treatment group and will be presented by Anatomical Therapeutic Chemical drug classes using the latest version of the WHO drug dictionary.

Treatment Compliance	
No analyses are planned to assess treatment compliance, given that participants will receive study intervention directly from the investigator or designee at the study site, under medical supervision (Section 6.4).

Additional imputation methods may be considered for all endpoint types.

Estimands for Double-Blind Treatment Period

Endpoints	Estimand strategy	Estimand description	Use post-discontinuation data?	Imputation	Possible analysis method (estimator)
Primary endpoint and all other continuous efficacy and PRO endpoints	Hypothetical efficacy	Mean change from baseline (and mean scores) had all subjects remained on randomized treatment.	No, only use data up until discontinuation	Participants who discontinue study intervention have remaining data imputed* to reflect the expected outcome had the subject remained on the study treatment without using restricted medications** (assume missing at random [MAR])	MMRM model under MAR is applied to the data prior to treatment discontinuation

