All dichotomous efficacy and	Composite responder	Proportion of responders where	No, only data up until discontinuation	Participants who start restricted medication** or discontinue study	Endpoint definition effectively

Endpoints	Estimand strategy	Estimand description	Use post-discontinuation data?	Imputation	Possible analysis method (estimator)
PRO endpoints		participants who start restricted medication or discontinue study intervention are considered treatment failures	is required to define endpoint	intervention are defined as nonresponders	gives complete data

*Note: No actual imputed value per participant, mixed model used to derive result at treatment group level.

** Restricted medications include prohibited medications (Section 6.5.2) and permitted medications above the allowable dose range (Section 6.5.1).

Any change to the data analysis methods described in the protocol will require an amendment only if the change affects a principal feature of the protocol. Any other change to the data analysis methods described in the protocol, and the justification for making the change, will be described in the SAP and the clinical study report (CSR). Additional exploratory analyses of the data will be conducted as deemed appropriate.

The SAP will be finalized prior to unblinding. It will include a more technical and detailed description of the statistical analyses described in this section.

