The primary clinical question of interest is: What is the intervention difference in change from baseline of DAS28-CRP after 12 weeks of intervention in participants with Moderately to Severely Active Rheumatoid Arthritis before intervention discontinuation for any reason and before initiation of rescue intervention or change in background intervention? The primary comparison will be assessed using a hypothetical efficacy estimand strategy to address the intercurrent event of early discontinuation where the mean change from baseline will be evaluated using only data up until discontinuation as if all subjects remained on randomized treatment.

The estimand is described by the following attributes:

Population: participants with Moderately to Severely Active Rheumatoid Arthritis. Further details can be found in Section 5.

Endpoint: change from baseline to week 12 in DAS28-CRP

Treatment condition: the randomized treatment without rescue medication or change in background medication (treatment policy strategy). Further details on study interventions and concomitant, including rescue, interventions can be found in Section 6.

The 2 intercurrent events “intervention discontinuation for any reason” and “initiation of rescue intervention or change in background intervention” are both addressed by the treatment condition of interest attribute. There are no remaining intercurrent events.

Population-level summary: difference in mean changes between intervention conditions

Rationale for estimand: The data collected after the treatment discontinuation or post-rescue medication will not represent the true efficacy effects.

Secondary estimands

1) ACR 20/50/70

The clinical question of interest is for the secondary objective regarding Moderately to Severely Active Rheumatoid Arthritis: What is the intervention difference in the percentage of participants achieving ACR20/50/70 after 12 weeks of intervention in participants with Moderately to Severely Active Rheumatoid Arthritis before intervention discontinuation for any reason and before initiation of any interventions affecting ACR20/50/70?

The estimand is described by the following attributes:

Population: participants with Moderately to Severely Active Rheumatoid Arthritis. Further details can be found in Section 5.

Endpoint: achievement of ACR 20/50/70 at week 12

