2.1. Multiplicity Adjustment

This is a proof of concept study. No adjustments will be made to adjust the performed efficacy analysis for multiplicity.

3. Analysis Sets

The following analysis data sets are defined to estimate the estimands defined in the protocol and to address safety.

Analysis Data Sets	Description
Full Analysis Set (FAS) for the primary estimand and for the secondary estimand for the secondary objective	
• All participants randomly assigned to study intervention and who take at least 1 dose of study intervention. Participants will be included in the analyses according to the planned intervention• For participants who discontinue study intervention and/or receive rescue therapy, post-discontinuation or post-rescue observations will not be included.
Safety analysis set to be used for safety assessments	
• All participants who are exposed to study intervention. Participants will be included in the analyses according to the intervention they actually received.• All observed data will be included in the analysis set.
Pharmacokinetic(PK) analysis set to be used for PK assessments	
• All participants randomly assigned to study intervention and who take at least 1 dose of study intervention and have PK data available.• All observed data until discontinuation of intervention will be included in the analysis set.

4. Statistical Analyses

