4.3.2. Main analytical approach

Observed values at baseline and changes from baseline to Week 12 endpoint in DAS28-CRP will be summarized by treatment arm and provided as listing.

A restricted maximum likelihood based, MMRM analysis will be used to analyze the primary endpoint. The MMRM model will include treatment, strata (previous RA therapy population), baseline value, visit, treatment-by-visit interaction in the model as fixed factors, and patient as a random factor. An unstructured covariance matrix will be used to model the within-subject errors. If this analysis fails to converge, other structures will be tested (in this order: Toeplitz, Autoregressive with heterogeneity, and Compound Symmetry). The Kenward-Roger approximation will be used to estimate denominator degrees of freedom. Significance tests will be based on least squares means and Type III tests. The data on or after the treatment discontinuation will not be included in MMRM analysis.

For participants who discontinue study intervention and/or receive rescue therapy, post-discontinuation or post-rescue observations will not be included.

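### The primary question is posed before any change in background therapy, but the MMRM keeps data after such a change, rescue is undefined, and the strategy label points the other way

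*SAP*

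**What the plan says.** **The question.** SAP 1.1 (primary estimand) asks for the effect on DAS28-CRP at Week 12 before discontinuation for any reason and "before initiation of rescue intervention or change in background intervention". It gives the treatment condition as "the randomized treatment without rescue medication or change in background medication (treatment policy strategy" and states that this condition takes care of both intercurrent events. The rationale is that later data do not show true efficacy. For early discontinuation, the same section calls the strategy hypothetical.

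**The data rule.** SAP 3 (Analysis Sets, full analysis set): "For participants who discontinue study intervention and/or receive rescue therapy, post-discontinuation or post-rescue observations will not be included". SAP 4.3.2 repeats the rule for the primary MMRM: "post-discontinuation or post-rescue observations will not be included". Neither place mentions a background change.

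**The protocol.** The estimand table in Protocol 9.4.1 describes the outcome to be reflected for participants who discontinue as the one "had the subject remained on the study treatment without using restricted medications". Its estimator is: "MMRM model under MAR is applied to the data prior to treatment discontinuation". A footnote explains: "Restricted medications include prohibited medications (Section 6.5.2) and permitted medications above the allowable dose range (Section 6.5.1".

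**Binary endpoints.** Under SAP 4.1, a participant who breaks the concomitant-medication rules counts as a nonresponder.

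**Backup analyses.** SAP 4.3.3 and 4.3.4 plan no sensitivity and no supplementary analysis of the primary endpoint.

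**The concern.** The question covers three things: discontinuation, rescue and background change. The data rule acts on two of them, and one of those two has no content. SAP 1.1 points to a Section 6 for details of rescue, but SAP 6 holds demographics, compliance and registry analyses, and Protocol 6 describes no rescue regimen. A programmer cannot tell which medication records should cut off a participant's data.

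A participant whose background therapy changes during Period 1 without stopping study drug would therefore contribute the later DAS28-CRP values to the primary analysis, although the question says it is about the effect before that change. If such changes differ between arms in frequency or effect, the primary difference no longer estimates what SAP 1.1 describes, and no planned analysis would show it.

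**Working it through.** **Step 1. Which background changes escape the data rule?**

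| Event in Period 1 | What the documents do | Later DAS28-CRP in the MMRM? |
|---|---|---|
| New agent of proven efficacy in RA | Protocol 7.2: participant leaves the study first | No, already lost through discontinuation |
| csDMARD change planned in advance | Exclusion criterion 30: not enrolled | Not applicable |
| Unforeseen intra-articular steroid injection | Protocol 6.5.1: recorded as a deviation | Yes |
| New or increased NSAID | Protocol 6.5.1: barred, but no discontinuation prescribed | Yes |
| Unplanned csDMARD or oral steroid change within the dose cap | Departs from the stability rules (criteria 10 and 30, Protocol 6.5.1); no discontinuation prescribed | Yes |

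Where some other concomitant drug is needed, Protocol 6.5 leaves discontinuation to the investigator in consultation with the sponsor, so it is not automatic. The restricted-medication definition does not catch the last three rows reliably. Protocol 6.5.2 lists only vaccines, and a change that stays within the dose cap is not above range. Yet the same departures from the Section 6.5 rules make a participant a nonresponder for ACR20.

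**Step 2. Reproduce the planned power.** Inputs from SAP 5: mean changes −1.80 and −0.75, so D = 1.05; SD 1.25; 40 versus 20 participants; two-sided α 0.05.

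- SE = 1.25 × √(1/40 + 1/20) = 0.342
- Noncentrality = D / SE = 1.05 / 0.342 = 3.07, with 58 df
- Power = 85.5% (noncentral t), or 86.6% by normal approximation. Both agree with the stated figure of more than 80%.

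Power reaches 80% at D of about 0.976.

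**Step 3. Illustrate the effect of keeping the data.** Let q be the share with a background change and g their extra DAS28-CRP improvement, with SD unchanged. Then D = 1.05 − g × (q_placebo − q_active). The documents give neither q nor g, so every row rests on assumed values.

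| g | q placebo / active | D | Power |
|---|---|---|---|
| 0.5 | 10% / 10% | 1.05 | 85.5% |
| 0.5 | 10% / 5% | 1.025 | 83.8% |
| 0.5 | 20% / 10% | 1.00 | 81.9% |
| 0.5 | 15% / 0% | 0.975 | 80.0% |
| 0.5 | 20% / 0% | 0.95 | 77.9% |
| 0.5 | 5% / 10% | 1.075 | 87.0% |
| 1.05 | 10% / 5% | 0.998 | 81.7% |
| 1.05 | 20% / 10% | 0.945 | 77.5% |
| 1.05 | 20% / 0% | 0.84 | 67.5% |

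**Step 4. Cost of excluding the data.** Worst case: every affected Week 12 value is lost, nothing is recovered from earlier visits, and D stays at 1.05.

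| Lost placebo / active | n placebo / active | Power |
|---|---|---|
| 10% / 5% | 18 / 38 | 82.2% |
| 20% / 10% | 16 / 36 | 78.3% |
| 30% / 15% | 14 / 34 | 73.6% |

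The MMRM would recover part of this loss from earlier visits.

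**The case against.** **The SAP may intend to keep these data.** The treatment policy label, taken literally, would retain values after a background change. A reader might infer that the estimand plainly removes background changes; the label prevents so firm a reading. But it does not rescue the plan. Treatment policy would also retain post-rescue values, which the rule drops, and it contradicts both the wording of the question and the rationale. The plan as written implements neither strategy in full.

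**Rescue may be shorthand for both.** SAP 1.1 counts rescue or background change as a single intercurrent event, and its rationale shortens this to rescue alone. Loose drafting is plausible. It still leaves the trigger undefined.

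**The protocol does not order the exclusion.** A reader might infer from the words "without using restricted medications" that the protocol requires the MMRM to drop data after restricted medication. It does not. The phrase describes the counterfactual for participants who discontinue. Only the row for dichotomous endpoints makes starting restricted medication an event in its own right.

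**Dilution is not certain.** It needs more frequent or stronger intensification on placebo. Equal shares with equal gain cancel, an excess on active inflates the difference, and reductions in therapy act the other way. A reader could assume 15% on placebo, none on active and a 1.0-point gain, which gives D = 0.90 and 73.4% power. That gain is about 95% of the whole assumed drug effect (1.0/1.05), and nothing in the documents supports it.

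**Conduct rules limit the size.** Criterion 30, Protocol 6.5.1 and Protocol 7.2 bar or pre-empt most changes. What remains is mainly protocol deviations over 12 weeks. This stands, and it limits the size without closing the gap.

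**Conclusion.** The mismatch holds on the text. The stated question stops at a background change, the full analysis set and MMRM rules do not, rescue is undefined, and the strategy label conflicts with the question. The effect on the result is possible but not established. The retained data may bias the 700 mg–placebo difference, most plausibly toward zero if placebo participants intensify more.

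The margin is narrow. A net dilution of about 0.075 DAS28-CRP points takes power from 85.5% to 80.0%. This rests on the assumed shares and gain, an unchanged SD, and a t-test standing in for the MMRM.

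The reason to act is not power. With 20%/10% affected and a 0.5-point gain, keeping the data gives 81.9% and the worst case of excluding them gives 78.3%. The reason is that the primary analysis should estimate the quantity that SAP 1.1 states. It should be corrected before any unblinding, because settling it afterwards would be open to the charge of being data-driven.

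**What to change.** 1. **SAP 1.1:** remove the treatment policy label for rescue and background change. The hypothetical strategy matches the stated question and its rationale.
2. **One event list:** define it to cover rescue, restricted medications as in Protocol 9.4.1, and any change in background csDMARD, corticosteroid or NSAID therapy that departs from the stability rules of Protocol 6.5.1 and criteria 10 and 30. Pointing only to the not-permitted column of 6.5.1 would be too narrow, because it has entries only for NSAIDs and corticosteroids.
3. **SAP 3 and 4.3.2:** exclude observations after the first of permanent discontinuation or a listed event.
4. **Flagging:** identify events from concomitant-medication and deviation records while blinded, before any unblinding, including the interim analysis.
5. **SAP 4.1:** leave the nonresponder rule as it is. It already covers all breaches of the concomitant-medication rules, and tying it to a list could narrow it.
6. **SAP 4.3.3:** add a sensitivity analysis of the primary endpoint that keeps the data after a background change.

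The cost is SAP wording, a blinded medication flag and one extra model run. Patient management does not change. Slightly more data become missing: losing 10% of placebo and 5% of active Week 12 values leaves about 82% power at worst, before the MMRM recovers anything from earlier visits.

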4.3.3. Sensitivity Analysis

No sensitivity analysis will be performed.

4.3.4. Supplementary analyses

No supplementary analysis will be performed.

4.4. Secondary Endpoints/Estimands Analysis

4.4.1. Key Secondary Endpoints

4.4.1.1. Definition of endpoint(s)

The secondary endpoints include:

- Proportion of participants achieving ACR20, ACR50, and ACR70
- Change from baseline for physician-assessed individual components:
 - 68 tender joint count
 - 66 swollen joint count
 - physician's global assessment of disease activity (VAS)
- Change from baseline for mean SDAI
- Change from baseline for mean CDAI
- Change from baseline for Individual components of the ACR core set:
 - patient's global assessment of disease activity (VAS),
 - patient's global assessment of arthritis pain
 - (VAS), and
 - patient's assessment of physical function (HAQDI)
 - Change from baseline for SF-36

4.4.1.2. Main analytical approach

4.4.1.2.1 ACR20

The frequency and percentage of patients achieving ACR20 response will be summarized by treatment arm at each post-baseline visit. A logistic regression model will be used to test the treatment difference of each LY dose versus placebo at each post-baseline visit with treatment group, baseline disease activity, and previous RA therapy population as model covariates. Baseline DAS28-CRP score will be used as the baseline variable. NRI as described in Section 4.1 will be used to impute missing data for ACR20 in patients who were Week 12 non-responders or who discontinued prior to Week 12.

The Kaplan-Meier estimator will be used to summarize time to ACR20 response over 12 weeks and a plot by treatment arm will be presented. Week 12 non-responders will be censored on the date of the Week 12 visit. All patients ongoing at Week 12 and who have not yet responded will be censored on the date of the Week 12 visit. A Cox proportional hazards model will be used to test the treatment comparison between each LY dose and placebo in time to ACR20 response over 12 weeks.

For participants who discontinue study intervention and/or receive rescue therapy, post-discontinuation or post-rescue observations will not be included.

Subjects with ACR20 response will also be listed.

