Treatment condition: the randomized intervention without any other interventions (treatment policy strategy). Further details on study interventions and concomitant, including rescue, interventions can be found in Section 6.

The 2 intercurrent events intervention discontinuation for any reason and any interventions affecting ACR 20/50/70 are both addressed by the treatment condition of interest attribute. There are no remaining intercurrent events.

Population-level summary: difference in percentage of participants achieving ACR 20/50/70 at week 12 between intervention conditions

Rationale for estimand: The data collected after the treatment discontinuation or post-rescue medication will not represent the true efficacy effects.

2) Change from baseline in TJC, SJC, PhGADA_VAS, PaGADA_VAS, patient's global assessment of arthritis pain (VAS), HAQ-DI, SF-36, and mean scores of SDAI and CDAI

The clinical question of interest is for the secondary objective regarding Moderately to Severely Active Rheumatoid Arthritis: What is the intervention difference in change from baseline of TJC, SJC, PhGADA_VAS, PaGADA_VAS, patient's global assessment of arthritis pain (VAS), HAQ-DI, SF-36, and mean scores of SDAI and CDAI after 12 weeks of intervention in participants with Moderately to Severely Active Rheumatoid Arthritis before intervention discontinuation for any reason and before initiation of rescue intervention or change in background intervention?

The estimand is described by the following attributes:

Population: participants with Moderately to Severely Active Rheumatoid Arthritis. Further details can be found in Section 5.

Endpoint: change from baseline to week 12 in TJC, SJC, PhGADA_VAS, PaGADA_VAS, patient's global assessment of arthritis pain (VAS), HAQ-DI, SF-36, and mean scores of SDAI and CDAI

Treatment condition: the randomized treatment without rescue medication or change in background medication (treatment policy strategy). Further details on study interventions and concomitant, including rescue, interventions can be found in Section 6.

The 2 intercurrent events “intervention discontinuation for any reason” and “initiation of rescue intervention or change in background intervention” are both addressed by the treatment condition of interest attribute. There are no remaining intercurrent events.

Population-level summary: difference in mean changes between intervention conditions

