1.2. Study Design

This is a Phase 2, proof-of-concept, placebo-controlled, double-blind, randomized study in adult participants with moderately to severely active RA who have had an inadequate response to csDMARDs, or to bDMARDs/tsDMARDs. Participants will be administered LY3462817 or placebo IV Q4W.

Screening Period (Visit 1, Days -42 to -1)

Participants will sign the informed consent document(s) at Visit 1, prior to completion of any procedures. Participants will be evaluated for study eligibility ≤ 42 days prior to the baseline visit (Visit 2).

Period 1: Double-blind Treatment (Visits 2 to 6; 12 weeks)

At the baseline visit (Visit 2), participants who fulfill the eligibility criteria will be randomized to receive LY3462817 700 mg, LY3462817 300 mg, or placebo in an allocation ratio of 2:1:1. The double-blind treatment period will establish the clinical efficacy and safety of LY3462817. The study will be evaluated for the primary objective at the end of the double-blind treatment period.

Period 2 (Visits 6 to 10; 12 weeks)

In Period 2, all subjects will receive LY3462817 to assess safety and tolerability data and explore clinical activity with additional dosing. At Week 14, participants will be evaluated for clinical benefit.

Posttreatment Safety Follow-up Period (Visits V801 and 802; 12 weeks)

Following Period 2, participants will be followed posttreatment for 12 weeks to assess safety, study drug exposure, and clinical disease activity measures.

2. Statistical Hypotheses

For the primary estimand with primary endpoint, change from baseline to week 12 in DAS28-CRP, the following 2 (confirmatory) 1-sided hypotheses are planned to be tested for LY3462817 700 mg versus placebo. Let the mean treatment difference be defined as $\mu = (\text{LY3462817 700 mg} - \text{placebo})$.

$H_0: \mu \geq 0.0$ against $H_a: \mu < 0.0$

Operationally the hypotheses will be evaluated by 2-sided tests.

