4.1. General Considerations

The independent variable, previous RA therapy population, is defined as only csDMARD experienced or bDMARD/tsDMARD experienced participants. Unless otherwise indicated in the statistical analysis plan (SAP), the analyses will be conducted as follows:

Analysis for	Description
Primary and secondary endpoint analyses comparing LY3462817 to placebo	Tested at a 2-sided level of 0.05 for frequentist analyses
Adjustments for multiplicity	None to be performed
Baseline	Defined as the last available value before the first dose of study intervention for both efficacy and safety analyses. In most cases, this value will be what is recorded at the randomization visit (Visit 2).
Change from baseline	Will be calculated as the visit value of interest minus the baseline value.
Efficacy and patient-reported outcome (PRO) analysis	Analysis models may contain the independent variables such as treatment group, baseline disease activity, and previous RA therapy population. Endpoint analyses will use the FAS unless otherwise specified.
Dichotomous responder endpoints	Missing data will be imputed using the nonresponder imputation (NRI) method. Will be analyzed using a logistic regression model with treatment group, baseline disease activity, and previous RA therapy population as model covariates.
NRI analysis	Participants will be considered nonresponders if: 
 • they do not meet all the clinical response criteria • they are noncompliant with concomitant medication rules

	
 • they permanently discontinue study intervention at any time before the end of the treatment period for any reason, or • they are randomized and do not have at least 1 postbaseline observation.
Continuous efficacy endpoints	
Mixed-effects model for repeated measures (MMRM) will be used.
 
The MMRM model will include treatment, strata (previous RA therapy population), baseline value, visit, treatment-by-visit interaction in the model as fixed factors, and patient as a random factor.
 
An unstructured covariance matrix will be used to model the within-subject errors. If this analysis fails to converge, other structures will be tested (in this order: Toeplitz, Autoregressive with heterogeneity, and compound symmetry.).
 
The Kenward-Roger approximation will be used to estimate denominator degrees of freedom. Significance tests will be based on least squares means and Type III tests.

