4.9. Changes to Protocol-Planned Analyses

There is no change to protocol-planned analyses.

5. Sample Size Determination

Approximately 80 participants will be randomly assigned to study intervention. At the completion of the study, approximately 40 participants will have been randomized to LY3462817 700 mg and 20 participants will have been randomized to LY3462817 300 mg and placebo during the double-blind treatment. All randomized participants in FAS will be considered evaluable.

Assuming -1.80 and -0.75 as the DAS28-CRP change from baseline for LY3462817 700 mg and placebo, respectively, with standard deviation equal to 1.25, a 2-sided t-test with alpha = 0.05 has greater than 80% power to detect a statistically-significant difference in DAS28-CRP change from baseline at Week 12.

6. Supporting Documentation

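### Responder endpoints are tested by ordinary logistic regression against about 20 placebo participants with no provision for a zero cell, and the ACR difference in percentages at Week 12 has no planned confidence interval

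*SAP*

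**What the plan says.** - **Model.** SAP 4.4.1.2.1 (ACR20) reads "A logistic regression model will be used to test the treatment difference of each LY dose versus placebo at each post-baseline visit". The covariates named there are treatment arm, a baseline variable (the DAS28-CRP score) and the prior-therapy stratum. SAP 4.4.1.2.2 carries this over to ACR50 and ACR70. SAP 4.5.1 to 4.5.4 use the same kind of model for remission and low disease activity by DAS28-CRP, DAS28-ESR, SDAI and CDAI.
- **Level.** Primary and secondary comparisons are "Tested at a 2-sided level of 0.05 for frequentist analyses" (SAP 4.1), with no multiplicity adjustment.
- **Arm sizes.** Randomisation is to "LY3462817 700 mg, LY3462817 300 mg, or placebo in an allocation ratio of 2:1:1" (SAP 1.2), about 80 participants in all. SAP Section 5 says that "20 participants will have been randomized to LY3462817 300 mg and placebo during the double-blind treatment", which with the 2:1:1 ratio means about 20 in each of those two arms and 40 on 700 mg.
- **Estimand.** For ACR20/50/70, SAP 1.1 gives the population-level summary as the "difference in percentage of participants achieving ACR 20/50/70 at week 12 between intervention conditions".
- **Missing data and fallbacks.** Nonresponder imputation applies (SAP 4.1). The MMRM has an ordered list of alternative covariance structures if it fails to converge; the logistic model has no equivalent. SAP 4.4.1.3 and 4.4.1.4 plan no sensitivity or supplementary analysis for the secondary endpoints.
- **Fisher's exact test.** SAP 4.1 makes it the default for categorical comparisons unless something else is specified. For the responder endpoints, logistic regression is specified.

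**The concern.** No penalised or exact version is named, so the natural reading is ordinary maximum likelihood. With 20 placebo participants, an uncommon response can leave that arm with no responders, and nonresponder imputation makes this somewhat more likely. The data are then separated on treatment and the maximum-likelihood odds ratio is infinite. What is reported depends on which test the software prints and where its iterations stop, and the SAP settles neither.

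At stake is a usable test for the less common responses. A clear difference between arms could come out as p near 1 under one default, or with too small a p-value under another.

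The second matter does not depend on rates. For ACR20/50/70 at Week 12 the declared summary is a difference in percentages. Percentages are tabulated by arm, but no difference with an interval is planned, and the logistic coefficient is on another scale.

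**Working it through.** **1. The plan's own figure.** The only sizing is for the primary endpoint: "Assuming -1.80 and -0.75 as the DAS28-CRP change from baseline for LY3462817 700 mg and placebo, respectively, with standard deviation equal to 1.25". SE = 1.25 × √(1/40 + 1/20) = 0.342; noncentrality = 1.05 / 0.342 = 3.07; power of the two-sided t-test with 58 df = 85.5%. The claim that the test "has greater than 80% power to detect a statistically-significant difference" reproduces. No power is stated for any responder endpoint.

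**2. How likely is a zero placebo cell?** P(0 of 20) = (1 − p)^20. Neither document gives a response rate, so p is an assumption, shown over a range.

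| Assumed placebo rate | P(0/20) |
|---|---|
| 2% | 67% |
| 5% | 36% |
| 10% | 12% |
| 15% | 4% |
| 20% | 1.2% |
| 30% | 0.1% |

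**3. What each test does with 0/20 placebo against 10/40 on 700 mg** (treatment term only):

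- *Wald.* The log odds ratio diverges. Stopping the fit at 8, 15 and 25 iterations gives an SE of 22, 738 and about 109,489, and p = 0.72, 0.98 and 1.00. The result depends on the stopping point.
- *Likelihood ratio, unpenalised.* Full model: 10 ln 0.25 + 30 ln 0.75 = −22.493. Null model: 10 ln(1/6) + 50 ln(5/6) = −27.034. Statistic = 2 × 4.540 = 9.08 on 1 df, p = 0.0026.
- *Firth.* Fitted proportions are 0.5/21 and 10.5/41; odds ratio = (10.5/30.5) / (0.5/20.5) = 14.1; penalised likelihood-ratio statistic 6.59, p = 0.010.
- *Fisher's exact test.* p = 0.023.

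The 300 mg comparison has the same weakness: 0/20 against 6/20 gives Fisher p = 0.020 and no usable Wald result.

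**4. Rejection probabilities, 20 against 40, by exact enumeration** at two-sided 0.05, treatment term only, all rates assumed:

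| Placebo v 700 mg rate | Wald | Likelihood ratio | Firth | Fisher |
|---|---|---|---|---|
| 2% v 20% | 1% | 69% | 52% | 42% |
| 5% v 30% | 20% | 75% | 67% | 64% |
| 10% v 30% | 18% | 48% | 40% | 37% |
| 20% v 40% | 29% | 36% | 33% | 29% |
| 10% v 10% (type I error) | 1.8% | 7.4% | 3.5% | 2.8% |

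Over equal rates of 2% to 30%, type I error is 0.3% to 4.7% for Firth and 0.3% to 3.6% for Fisher. At 5% v 30% the Wald test loses 67 − 20 = 47 points of power against Firth, more than the 36% chance of a zero cell, so part of the loss arises when placebo has only a few responders.

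In a 2,000-run simulation of the three-arm model with a continuous baseline and a binary stratum, the Wald test never rejected when placebo had no responders. Covariate adjustment does not remove the problem.

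**5. Scale.** With placebo rate p, an odds ratio of 3 implies active odds of 3p/(1 − p). At p = 2%, 10% and 30% the difference is 3.8, 15 and 26 percentage points. The logistic coefficient alone therefore does not give the difference that SAP 1.1 defines. In the 0/20 v 10/40 example that difference is 25 points. The Wilson limits are 14.2% to 40.2% for 10/40 and 0% to 16.1% for 0/20, so the Newcombe 95% CI runs from 25 − √(10.8² + 16.1²) = 6 to 25 + √(15.2² + 0²) = 40 points. The interval exists with a zero cell.

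**The case against.** The strongest reply is that the SAP names neither a Wald test nor an odds ratio. A reader might infer that the plan commits the trial to reporting a clear difference as p near 1. It does not: the likelihood-ratio test of the same model gives 0.0026 in the worked example. That stands, and the gap is properly that the test is unspecified. But neither common default is sound here, because the Wald test cannot reject with a zero placebo cell and the unpenalised likelihood-ratio test exceeds its nominal level at low rates.

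Second, the section quoted concerns ACR20, where a zero cell may be very unlikely: about 1% or less if the placebo rate at Week 12 is 20% to 30%. That also stands. The concern is for endpoints or visits with placebo rates of about 10% or lower, plausibly ACR70, remission or the early visits, though the documents do not confirm those rates.

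Third, Fisher's exact test is already in SAP 4.1 and handles a zero cell. As worded, it yields wherever another method is specified, so it is the nearest fallback and not the planned one.

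Fourth, the percentages by arm are tabulated, so an unadjusted point difference can be read off, and a logistic fit can be standardised to percentages. Both are true; what is missing is a planned difference with its interval. Nor should the mismatch be extended to remission or low disease activity, for which SAP 1.1 states no population-level summary, or to ACR at earlier visits.

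Finally, these are secondary and exploratory endpoints in a proof-of-concept trial. That limits the consequence without removing the gap.

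**Conclusion.** The point holds in a limited form.

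- **Separation.** The responder analyses lack a test and a fallback that work when placebo has no responders. The size depends on an assumed placebo rate: the chance of 0/20 is 12% at 10%, 36% at 5% and 67% at 2%, but 1.2% or less at 20% and above. Within the low range the choice of test matters: at 5% v 30%, power is 20% for Wald, 67% for Firth and 64% for Fisher. These power figures are unadjusted and assume full arms of 20 and 40.
- **Estimand.** For ACR20/50/70 at Week 12 only, the declared difference in percentages has no planned interval estimate. This needs no assumption about rates.

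The documents do not support the stronger reading that responder testing fails across the board. The primary MMRM analysis of DAS28-CRP, its stated power and the interim posterior probabilities for DAS28-CRP are unaffected. The change is worth making before unblinding but is not critical to the trial.

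**What to change.** In SAP 4.4.1.2.1 (hence 4.4.1.2.2) and 4.5.1 to 4.5.4, keep the covariates and specify Firth-penalised logistic regression with penalised profile-likelihood p-values, or exact logistic regression. Apply it in all cases, so that the method is not chosen after the cell counts are seen. For ACR20/50/70 at Week 12, add the risk difference for each dose against placebo with a 95% CI, either covariate-standardised from the model or by Newcombe's method, and name which.

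The cost is SAP wording and a few lines of code; conduct, data collection and sample size do not change. The downside is slight shrinkage of the Firth estimate. The choice between Firth and an exact method is partly preference, since Firth and Fisher have similar power at 5% v 30%; what matters is that one is named in advance.
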